Discrete Choice. Interdisciplinary research describes choice as a function of the relative expected value of the options at hand.^{61, 62} Further, an option’s anticipated value is derived from the integrated values of its individual attributes.^{63, 64} Widely used in consumer research, discrete choice experiments (DCEs) reveal the extent to which individual product attributes determine choice.⁶⁵ In DCEs, across several trials, participants chose their preferred option from a selection of products, each described as a set of attributes. The products/combinations of attributes presented in each trial are experimentally varied such that the relative importance of each attribute can be discerned using logistic regression. In tobacco regulatory science DCEs have been used

frequently to evaluate general preferences for cigarette and vaping device characteristics.⁶⁶⁻⁶⁹ Here, we will use the DCE method to investigate the contribution of nicotine content and flavor availability to choices between cigarettes and vaping devices.

OBJECTIVES

We are proposing a four condition ETM study to determine if banning NNC is sufficient for encouraging smokers to switch to potentially less harmful products or if the availability of higher nicotine and/or flavored alternative products (specifically e-cigarettes) are needed to achieve maximal reductions in smoking.

METHODS AND MEASURES

Overall Study Design

We propose to conduct a within-subjects, multi-session virtual lab study and validation field assessment to determine how the availability of flavored e-liquids affects product purchasing among cigarette smokers. Adult daily cigarette smokers (N=64) will be recruited for this study. After initial eligibility is assessed, participants will complete six virtual sessions (1 baseline, 4 experimental, and 1 follow-up) and three in person sessions with one field assessment to evaluate their tobacco use.

Design and Setting

Participants will be recruited from Winston-Salem, NC and the surrounding area using advertisements on public transit, community flyers, and social media.. In-person lab visits to drop off biosamples and pickup study products will be conducted at the Wake Forest Tobacco Control Center of Excellence located in Biotech Place in the Innovation Quarter.

Subject Selection Criteria

We anticipate recruiting up to 100 participants to achieve 64 completers.

Inclusion criteria:

1. 21+ years of age

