Discrete choice task 1: The Sawtooth Lighthouse Studio platform will host a discrete choice task (See DCE Questionnaire). First, participants will rate the appeal of cigarettes and e-cigarettes characteristics, which helps familiarize them with the product features that will be manipulated in the choice task. Next, the choice task will begin, and they will make several choices between a cigarette option and an e-cigarette option responding to a prompt that asks which they would rather use exclusively for the next week. Each cigarette vs e-cigarette trial will present different combinations of cigarette nicotine content, e-liquid nicotine content, and e-liquid flavor. Finally, the participant will complete follow-up questions about which characteristics most informed their choices. The data from this task will reveal how participants prioritize and make tradeoffs between product type, nicotine content, and flavor when forming preferences.

After completing the discrete choice procedure, participants will also be given the opportunity to sample the low and normal nicotine Spectrum investigational cigarettes available during the ETM (up to 4 puffs each). Other products will also be available on the ETM, but will not be available for sampling. These include: fruit, dessert, menthol, and tobacco flavored e-liquids; and mint, fruit and cinnamon flavored nicotine gum.

Virtual Visits 2-5

Participants will complete Virtual Visit 2 between 1 and 21 days after completing In-Person Lab Visit 1. Virtual Visits 2-5 will ideally be conducted four days in a row to reduce online task fatigue. However, visits may be scheduled up to 7 days apart.

The following assessment will be administered as an interview and entered into REDCap by the interviewer:

1. Timeline Follow Back (TLFB) Questionnaire, which will assess tobacco and nicotine product use since their last virtual visit.

Participants will complete the ETM task on the computer. If the participant needs assistance with navigating the online marketplace the research staff may screen share and allow the participant to verbally select the items that they would like to purchase. The products available on the ETM include:

- Spectrum cigarettes
- Fruit, dessert, mint and tobacco e-liquids (e.g., Vaporesso Xross Mini)
- Mint, fruit, and cinnamon nicotine gum (e.g., Nicorette).

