Participants will undergo one of four marketplace conditions during Virtual Visits 2-5, with the order of administration randomized across participants.

- Marketplace Condition 1 includes moderate nicotine content vape with all flavor e-liquids.
- Marketplace Condition 2 includes moderate nicotine content vape with tobacco e-liquids.
- Marketplace Condition 3 includes low nicotine content vape with all flavor e-liquids.
- Marketplace Condition 4 includes low nicotine content vape with tobacco e-liquids.

Staff will instruct participants to complete the ETM task as if they are purchasing the products from a retailer, and that one iteration of the task will be randomly selected and will determine which products they will use during the field assessment. In reality, we will randomly assign which condition is used (Condition 2 or 4) but will assign products based on when NNC were not available to simulate a nicotine content reduction policy.

For each marketplace condition, participants will complete 7 iterations of the ETM task in ascending order. The prices for NNC cigarettes on the ETM will be set at: \$0.12, \$0.25, \$0.50, \$1.00, \$2.00 per cigarette; in the 1st ETM condition, NNC cigarettes will be set at \$0.25 with no VLNC available to purchase to simulate current market status; while in the 6th ETM condition, NNC will be eliminated from the marketplace to simulate a nicotine content reduction policy. The costs for the other products will reflect average prices in NC and will not change during the task. For each task iteration, participants will receive individually-tailored account balances approximately equal to the money they would spend on cigarettes for seven days. They can purchase as many or few products as their account balance allows. Participants are not required to buy products from the ETM or can buy nicotine gum if they prefer. If they do not buy products from the ETM and do not use tobacco products during the field assessment, then they will receive their ETM account balance at Virtual Visit 6. This payment is delayed to reduce the likelihood that they will use this money to buy their preferred brand cigarettes, thus decreasing the validity of the ETM task.

Participants will be instructed to use only the products purchased from the ETM during the subsequent 7-day period after Virtual Visit 5 and told that we will assess adherence at Lab Visit 3.

In-Person Lab Visit 2

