In-Person Lab Visit 2 will be completed up to 48 hours after completing Virtual Visit 5. Participants will complete the COVID screener within 24 hours of their Lab visit via email or phone. Research staff will wear personal protective equipment during the visit including face masks and gloves. The participants will be required to wear facemasks when interacting with the staff. Temperature checks will be conducted immediately upon arrival using a thermal heat scanner.

Participants will provide CO readings be at least 6-feet away from other people, including the research staff, while they have their masks off.

Participants will be given the products they purchased during the ETM task and will be instructed to only use these products for the next seven days. They will also be given a urine collection cup and instructions for sample collection.

The field assessment validates the ETM task by having participants use the products in the real world, simulating the different regulatory environments. Actual product use enables us to measure their subjective experiences such as withdrawal, craving, or product satisfaction as well as assess changes in carbon monoxide exposure, a biomarker of harm, when using products other than menthol cigarettes. We will conduct between-subjects analyses comparing these secondary outcomes by marketplace condition.

Virtual Visit 6

Participants will complete Virtual Session 6 seven days after completing In-Person Lab Visit 2.

The following baseline assessments will be administered as an interview and entered into REDCap by the interviewer:

1. Timeline Follow Back (TLFB) Questionnaire which will assess past tobacco and nicotine product use since Virtual Visit 5.

The following surveys will be self-administered using REDCap:

1. Tobacco Policy Questionnaire
2. Minnesota Nicotine Withdrawal Scale
3. Questionnaire of Smoking Urges-Brief – Usual Brand Cigarette
4. Product Evaluation Scale – VLNC, E-Cigarette, Gum (whichever product(s) they select)
5. Perceived Health Risks Scale
6. Tobacco Product Interest Scale
7. Health Changes Questionnaire

Participants will complete the ETM task under the same marketplace condition from which they received their field assessment products. Exploratory pre-post field assessment analyses will examine how actual use of the products affects subsequent purchasing of those products.

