Research staff will conduct in-depth interviews with the participants to assess the following constructions: 1) decision-making during the ETM task; 2) use of alternative products during the field assessment; 3) product risk perceptions and; 4) opinions regarding possible tobacco control policies.

In-Person Lab Visit 3

In-Person Lab Visit 3 will be completed up to 48 hours after completing Virtual Visit 6. Participants will complete the COVID screener within 24 hours of their Lab visit via email or phone. Research staff will wear personal protective equipment during the visit including face masks and gloves. The participants will be required to wear facemasks when interacting with the staff. Temperature checks will be conducted immediately upon arrival using a thermal heat scanner. Participants will bring a first void urine sample, which will be banked for future biomarker analysis (e.g., total nicotine equivalents) and all of their used/unused products.

Participants will provide CO readings at least 6-feet away from other people, including the research staff, while they have their masks off. Participants will complete a second iteration of discrete choice task 1. Data from the two choice tasks will be compared within participants to see whether product use affected preferences.

All participants will be emailed a cessation manual and local smoking cessation resources.

Product adherence

To verify self-reported tobacco use, all used and unused products will be collected and counted at In-Person Lab Visit 3. Discrepancies between consumption stated on the TLFB versus consumption based on the products returned will be addressed. Non-adherence (i.e., using products not purchased from the ETM) will be assessed via the TLFB and qualitative interview with the importance of honest self-reporting emphasized. If participants report not using combusted tobacco, then CO readings < 6 ppm will verify their self-report.

Compensation

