Cross-price elasticity estimates will be calculated as the slope of the regression line (B_1) fit to log-transformed purchasing of each alternative product when offered at fixed prices (C) versus log-transformed menthol cigarette price (P): $\log C = B_0 + B_1 \log P$. Exploratory paired t-tests will compare product purchasing during the pre- and post-field assessment ETM task.

Attribute-importance will be generated from discrete choice response data using logistic regression. A utility range (the difference between a characteristic's highest and lowest estimated part-worth utility) will be calculated for device type, cigarette nicotine content, vaping device nicotine content and vaping device flavor availability. Part-worth utility refers to the relative

contribution of each level of a product characteristic on choice (ie, as approximated by the estimated coefficients in the model). The relative importance of each characteristic on making a choice will be calculated as the utility range for each characteristic, divided by the sum of all the characteristics' utility ranges.

Analysis of Exploratory Outcomes

Product use and biomarkers of exposure during the field assessment will be analyzed using linear regression or other appropriate regression models. The model for primary analysis of these data will include main effects for each of the two factors (for the ETM condition carried into the field assessment), and the corresponding baseline measure to improve precision. We will also test the two-way interaction between the two factors. If significant, the interaction will be included in the model; otherwise, it will be removed. We will also complete a secondary analysis that adjusted for age, race, sex, and other covariates that vary between treatment conditions. Biomarkers of exposure will be natural-log-transformed before analysis due to skewness. Key model assumptions will be evaluated for other endpoints and appropriate transformations will be considered if model assumptions are violated.

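### The pre-post marketplace and discrete choice comparisons are worded as effects of product use, but no group repeats the tasks without the field week

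*Combined protocol and SAP*

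**What the plan says.** **Marketplace (ETM) task.** The Virtual Visit 6 section sets the aim: "Exploratory pre-post field assessment analyses will examine how actual use of the products affects subsequent purchasing of those products". The test, in Analysis of Secondary Outcomes, is brief: "Exploratory paired t-tests will compare product purchasing during the pre- and post-field assessment ETM task". No term for field condition, visit or previous condition is named, and the text does not say whether the tests are pooled over conditions or run separately.

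**Stakes.** At Virtual Visits 2-5 staff tell participants that "one iteration of the task will be randomly selected and will determine which products they will use during the field assessment". For the repeat, the protocol specifies only the condition: "Participants will complete the ETM task under the same marketplace condition from which they received their field assessment products".

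**Schedule.** Overall Study Design gives all participants "three in person sessions with one field assessment to evaluate their tobacco use". The repeat comes after that week: "Participants will complete Virtual Session 6 seven days after completing In-Person Lab Visit 2". The only later contact is In-Person Lab Visit 3, where products are collected.

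**Discrete choice task.** It is run at In-Person Lab Visits 1 and 3. The stated purpose of the repeat is: "Data from the two choice tasks will be compared within participants to see whether product use affected preferences".

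**Randomization.** Field products come from Condition 2 or Condition 4, assigned at random. Both offer tobacco-flavored e-liquid only; they differ in e-liquid nicotine content (moderate versus low).

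**The concern.** Both comparisons ask a causal question of a single-group before-and-after design. Anything else that changes between the two runs is counted as an effect of use.

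For the ETM, several things change together. Before the field week, participants believe that a basket will be honored. Afterwards, no dispensing, use period or payout is described for the Visit 6 choices. The repeat is always the last ETM task, whereas the matching earlier task can fall at any of Visits 2-5. The primary model includes visit and previous-condition terms for this kind of influence; the paired t-test has neither.

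For the discrete choice task, no stake is described at either run, so that mechanism does not apply. Other influences do. The first run comes before any contact with the study cigarettes ("After completing the discrete choice procedure, participants will also be given the opportunity to sample the low and normal nicotine Spectrum") and before 4 × 7 = 28 marketplace iterations. A change in part-worths can reflect sampling, task exposure, time or use.

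At stake is the interpretation: a report could say that a week of use changed purchasing or preferences when the data show only that they changed.

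**Working it through.** The plan gives no power or effect size for the pre-post tests, so there is no stated figure to reproduce. The Power calculation covers the 2×2 purchasing factors only.

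**1. What coincides with pre/post in the ETM comparison**

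| Feature | Earlier task (Visits 2-5) | Visit 6 task |
|---|---|---|
| Stake described | One iteration decides the field products | None |
| Position | Any of four visits, randomized | Always last |
| Field week | Before it | After it, for everyone |

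Each row is aligned with the field week. Running the test separately within Condition 2 and Condition 4 leaves this alignment as it is.

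**2. Elapsed time from the matching ETM task to Visit 6**

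Inputs: Visits 2-5 ideally on four consecutive days but up to 7 days apart; Lab Visit 2 up to 48 hours after Visit 5; Visit 6 seven days after Lab Visit 2. Same-day Lab Visit 2 is taken as the minimum.

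- Shortest (field condition at Visit 5): 0 + 0 + 7 = 7 days.
- Ideal spacing, field condition at Visit 2: 3 + 2 + 7 = 12 days.
- Window limits, field condition at Visit 2: 3 × 7 + 2 + 7 = 30 days.

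**3. How often a paired test would be significant with no use effect**

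Inputs: n = 64 completers (Power calculation); two-sided 0.05, assumed because no level is stated; a non-use shift *d* in SD units of the paired difference, assumed because the documents give no value. The test statistic is noncentral t with n − 1 degrees of freedom and noncentrality *d*√n, which is 8*d* for n = 64.

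| *d* (assumed) | 8*d* | Significant, n = 64 | Significant, n = 32 (one condition) |
|---|---|---|---|
| 0.1 | 0.8 | 12% | 9% |
| 0.2 | 1.6 | 35% | 20% |
| 0.3 | 2.4 | 66% | 38% |
| 0.5 | 4.0 | 98% | 78% |

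Simulation of 20,000 trials agreed at the shifts checked (36% at 0.2 and 98% at 0.5 for n = 64). The lower rates at n = 32 reflect less power, not better attribution.

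**4. The randomized contrast**

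Compare change between Condition 2 and Condition 4, assuming 32 per group (a 1:1 ratio is not stated). If both groups share the same non-use shift, it cancels and the rejection rate stays at 5%. The detectable difference at 80% power is approximately (1.96 + 0.84) × √(2/32) = 0.70, or 0.71 SD of change with the t distribution. For the paired test in all 64 it is (1.96 + 0.84)/√64 = 0.35, or 0.36 SD with the t distribution. The contrast therefore detects only effects about twice as large, before covariate adjustment.

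**The case against.** The strongest reply is that the plan calls the ETM comparison exploratory in both places, that it is not in the outcome list, and that the primary objective concerns purchasing at Visits 2-5. This stands and keeps the severity low. It does not repair the causal wording. The discrete choice comparison carries no exploratory label, and discrete choice utilities are a listed secondary outcome.

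Several stronger readings are tempting but unsupported:

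- **That the Visit 6 task is known to be hypothetical.** The documents do not say what participants are told then. The missing stake is inferred from the schedule. If a stake exists, order, repetition and time still coincide with use.
- **That purchases will rise once nothing is delivered.** Tailored account balances cap spending in each iteration, and nothing says the cap is lifted at Visit 6. The direction of any bias is unknown.
- **That the plan pools the two conditions.** It does not say. The problem is the same either way.
- **That there is no comparison group of any kind.** There are two randomized field conditions. What is missing is a group that does not go through the field week.
- **That any one false-positive rate follows.** The rate depends wholly on the assumed shift.
- **That the first discrete choice run should follow the cigarette sampling.** That would give up the pre-sampling baseline and still leave 28 marketplace iterations within the change. It is a trade-off, not a correction.

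It is also fair to say that the randomized contrast answers another question. Participants choose their own baskets in both conditions, and use effects that are equal in the two groups cancel out.

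**Conclusion.** The point holds, at low severity. As designed, neither within-participant comparison can support a statement that product use changed purchasing or preferences. This rests on the schedule and on the absence of a non-use group, not on any numerical assumption. The size of the problem is not known from the documents: the range of about 12% to 98% for shifts of 0.1 to 0.5 SD is illustrative and assumes 64 completers and two-sided 0.05. The loss of stakes is a well-supported inference for the ETM task only. The primary analysis is not affected.

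**What to change.** 1. Keep the paired ETM and discrete choice comparisons as descriptive. Reword the Virtual Visit 6 and In-Person Lab Visit 3 sections so that they describe change across the field week without attributing it to use. It would also help to state what participants are told about their choices at Visit 6.
2. Add an exploratory regression of Visit 6 purchasing on randomized field condition (2 versus 4), adjusted for the pre-field purchase in the same condition. Do the same for post-field part-worths, adjusted for the pre-field value. The Analysis of Exploratory Outcomes already uses a baseline-adjusted regression by condition for product use and biomarkers.

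The cost is SAP and protocol wording; no visit or procedure changes. The downside is in what the added contrast can show: only the difference between experience under moderate and low e-liquid nicotine, with about 0.71 SD detectable before adjustment (32 versus 32 assumed) against 0.36 SD for the paired test.

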E-cigarettes have rapidly emerged as a commonly used non-combusted product in the U.S.^{34, 35} with a proposed rule by FDA that it they be deemed a "tobacco product" and regulated as such.³⁶ A study by Hatsukami and colleagues showed that approximately half of all smokers switched to VLNC cigarettes will try e-cigarettes when provided the opportunity and that there is a negative association between smoking VLNC cigarettes and use of alternative products.³⁷ However, we know little about how the characteristics of e-cigarettes impact VLNC use and, conversely, how nicotine reduction in cigarettes impacts the use of e-cigarettes with different characteristics. Both nicotine and non-nicotine factors may be important.

Nicotine. Nicotine delivered via e-cigarettes may serve a variety of functions that support its actions as a reinforcer and an appealing alternative to smoking VLNC cigarettes. Some e-cigarettes can deliver as much or more (among experienced users) nicotine as a traditional cigarette with a relatively rapid rate of absorption (T max < 5 min).³⁸ This pharmacokinetic profile suggests that e-cigarettes may have greater positive reinforcing effects than VLNC cigarettes.³⁹ E-cigarettes can also be used throughout the day to maintain nicotine levels that would otherwise fall by 95% or more once participants start using VLNC cigarettes.⁴⁰ Indeed, e-cigarettes reduce withdrawal symptoms in cigarette smokers,⁴¹⁻⁴⁵ and this suppression is dependent on the nicotine concentration of the e-liquid.⁴⁵ Relatedly, greater nicotine delivery may also result in increased risk of dependence on e-cigarettes.⁴⁶ Finally, nicotine also acts peripherally on receptors in the oropharyngeal cavity which may contribute to sensory effects (discussed below) that might generalize across products. Together, these data suggest that e-cigarettes that more effectively deliver nicotine may be more likely to function as both positive and negative reinforcers and more able to compete with the reduced reinforcing effects of VLNC cigarettes.

Non-nicotine factors. E-cigarettes have a somewhat unique feature relative to other alternative products - they provide sensorimotor stimuli similar to combusted cigarettes, including a smoke-

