Participants will be paid \$160 for completing the study. They will earn \$30 for completing Virtual Visit 1, \$15 per visit for completing Virtual Visits 2-5, \$20 for Virtual Visit 6, plus a \$50 bonus for completing the study. Participants who do not meet enrollment criteria at Virtual 1 will earn \$20 for attending the visit. Participants who start but do not complete the study will receive payments for the virtual visits attended. They will not receive the \$50 completion bonus. Participants will also be reimbursed up to \$20 per in-person lab visit for transportation costs.

ANALYSIS PLAN

Primary Outcome

- Number of cigarettes purchased (analyzed as raw data and using derived behavioral economic measures).

Secondary Outcomes

- E-liquid purchased (analyzed as raw data and using derived behavioral economic measures).
- Relative importance and utility data from discrete choice experiment
- Perceived Health Risk Scale scores
- Product Evaluation Scale scores
- Minnesota Nicotine Withdrawal Scale scores
- Questionnaire on Smoking Urges scores
- Tobacco Product Interest scores
- Tobacco Policy Questionnaire scores

Exploratory Outcomes

- Themes emerging from the qualitative interviews
- Product use during Field Assessment
- Biomarkers of exposure during Field Assessment

Sample Size/Estimation/Analysis

Statistical analysis plan

This ETM study will use a 2x2 factorial design. The primary objective will be to evaluate the effect of the two factors – e-liquid nicotine content (moderate vs. low) and e-liquid flavors (all flavors available vs. only tobacco flavor) – on purchasing behavior during virtual visits 2 – 5. Product use behavior, biomarkers of exposure, and other measures of smoking behavior during the field assessment will be evaluated in exploratory analyses.

Analysis of the Primary Outcome

The primary outcome will be the number of cigarettes purchased during the virtual visits. These data will be analyzed both in their raw form (i.e. the raw number of cigarettes purchased) and using derived behavioral economic measures. This is a within-subject design, with each participant providing data under all four factor combinations, and, for the raw data, each participant will provide data for all price combinations nested within a visit.

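### The field comparison of Conditions 2 and 4 is unbiased, but it is diluted by participants who buy no e-liquid; a contrast among e-liquid buyers should be pre-specified beside it

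*Combined protocol and SAP*

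**What the plan says.** The section on Virtual Visits 2-5 sets out the field allocation: "we will randomly assign which condition is used (Condition 2 or 4) but will assign products based on when NNC were not available". The two candidate marketplaces are "Marketplace Condition 2 includes moderate nicotine content vape with tobacco e-liquids" and "Marketplace Condition 4 includes low nicotine content vape with tobacco e-liquids". Both offer tobacco flavor only, and the prices of products other than NNC cigarettes are fixed, so as described they differ only in e-liquid nicotine. The relevant task iteration is the one where "NNC will be eliminated from the marketplace to simulate a nicotine content reduction policy". Participants may buy nicotine gum or nothing at all, so a basket without e-liquid is allowed.

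Under In-Person Lab Visit 2, participants receive what they bought and are told to use nothing else for seven days. The plan for withdrawal, craving, satisfaction and carbon monoxide is: "We will conduct between-subjects analyses comparing these secondary outcomes by marketplace condition". For field product use and biomarkers, Analysis of Exploratory Outcomes says "The model for primary analysis of these data will include main effects for each of the two factors". It adds the matching baseline measure and, in a secondary analysis, demographic and other covariates. Basket content is not named as a stratum, a covariate or a quantity to report.

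Analysis of the Primary Outcome describes a within-subject design, "with each participant providing data under all four factor combinations". Both candidate baskets are therefore on record before products are handed out.

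**The concern.** The assignment changes one thing: the nicotine level of the e-liquid on offer. Someone who declined e-liquid in the no-NNC iteration of both conditions goes home with very low nicotine content (VLNC) cigarettes, gum or nothing, whichever condition is drawn. That person adds variability to the comparison but little or no information about e-liquid nicotine in use.

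The all-participant estimate is then roughly the effect in e-liquid buyers multiplied by their share. A null result could be read as showing that e-liquid nicotine makes no difference in real use, when it may reflect how few participants had any e-liquid. The information needed to tell these apart is already collected, but the plan does not use it.

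In what follows, a buyer is a participant with e-liquid in the no-NNC basket of Condition 2 or of Condition 4.

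**Working it through.** **The plan's own figure.** There is none for the field comparison. The Power calculation section gives detectable effects (for example 0.45 at correlation 0.4) for the within-person purchasing analysis only. Nothing below depends on them.

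**Inputs**
- 64 completers (Power calculation). I assume 32 per field arm; the allocation ratio is not stated.
- Outcome SD 1 and two-sided 0.05: assumed.
- Effect d in buyers and zero in non-buyers: assumed.
- Buyer share b: not in the documents, so I use a range of 30% to 90%. The background says "approximately half of all smokers switched to VLNC cigarettes will try e-cigarettes when provided the opportunity", which is only a loose anchor for 50%.

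**Step 1: detectable effect with everyone affected.** SE = √(2/32) = 0.25. By the normal approximation, (1.96 + 0.84) × 0.25 = 0.70 SD for 80% power; the t-test gives 0.711 SD.

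**Step 2: all participants.** The average effect is b × d, so the effect needed in buyers is 0.711 / b. At b = 0.5 this is 0.711 / 0.5 = 1.42 SD.

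**Step 3: buyers only.** There are about 32b per arm. At b = 0.5 that is 16 per arm, and the t-test needs 1.02 SD.

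**Step 4: power at d = 1.0.** By the normal approximation at b = 0.5:
- All participants: Φ(0.5/0.25 − 1.96) = Φ(0.04) = 52%.
- Buyers: Φ(1/√(2/16) − 1.96) = Φ(0.87) = 81%.

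Simulated t-tests give somewhat lower values. They allow for the small samples and, in the all-participant analysis, for the extra spread from mixing buyers and non-buyers in one arm. The power columns below are simulated; repeated runs agree to about one percentage point.

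| Buyer share | Needed in buyers, all-participant analysis | Needed in buyers, buyer analysis | Power at 1.0 SD, all | Power at 1.0 SD, buyers |
|---|---|---|---|---|
| 30% | 2.37 SD | 1.36 SD | 20% | 52% |
| 50% | 1.42 SD | 1.02 SD | 46% | 77% |
| 70% | 1.02 SD | 0.86 SD | 75% | 90% |
| 80% | 0.89 SD | 0.80 SD | 85–86% | 94% |
| 90% | 0.79 SD | 0.75 SD | 94% | 96–97% |

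At a smaller effect of 0.7 SD with 50% buyers, power is about 27% for all participants and 48% for buyers.

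**Step 5: validity of the buyer contrast.** The indicator uses both baskets. Both are filled before hand-out, by participants who do not know which will be used. It is therefore a baseline variable, and randomization holds within it. With no true effect, simulated rejection rates were about 5% for both analyses. Using the received basket instead would not be safe: a person tempted only by the moderate-nicotine liquid would count as a buyer in one arm and not in the other.

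**The case against.** The strongest reply is that the all-participant contrast is the right estimand. The field week is meant to mimic regulatory environments. Under such a policy some smokers would not vape, and their outcomes belong in the policy effect. This stands. A reader might infer that the planned comparison is biased, or that the buyer contrast should replace it as the lead analysis. The documents support neither: the comparison is randomized, and the buyer contrast answers a different question in fewer people.

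A second tempting inference is that the effect in non-buyers is zero by construction. It is not. The two baskets come from separate sessions, and amounts of VLNC cigarettes or gum may differ between them. The purchasing task at Virtual Visit 6 is also repeated under the assigned condition. Near zero is a reasonable expectation for the field outcomes, but exact zero is an assumption behind every power figure above.

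Third, the buyer share may be high. Eligibility requires willingness to use other tobacco products and having tried vaping, and the background reports that e-cigarettes were the most frequent choice in the pilot study. The figure of about half concerns trying e-cigarettes in another study, not buying e-liquid in either of two baskets. At 80–90% buyers the gain is small.

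Fourth, the buyer contrast is not well powered either. With 50% buyers it still needs about 1.0 SD for 80% power, and with 30% buyers it rests on about 19 people (0.3 × 64 = 19.2).

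Finally, this comparison is not the only evidence on real use. The plan also has interviews, a repeated discrete choice task and a pre-post purchasing comparison.

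**Conclusion.** The concern holds as a matter of dilution and lost power, not of bias. The all-participant contrast between Conditions 2 and 4 is a sound policy-level result, but a weak test of whether e-liquid nicotine matters to those who have e-liquid to use. With a 1.0 SD effect in buyers, the difference in power is about 32 percentage points at a 30% buyer share (52 − 20), 31 at 50% (77 − 46), 15 at 70% (90 − 75), and 2 to 3 at 90%. These figures rest on 32 per arm, SD 1, two-sided 0.05 and zero effect in non-buyers. The true share will be known only once Virtual Visits 2-5 are complete.

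Severity is low: the primary objective is purchasing at Virtual Visits 2-5, and the field outcomes are secondary or exploratory. Pre-specification is worthwhile because the same subgroup, chosen after the results are seen, would carry much less weight.

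**What to change.** - **Analysis of Exploratory Outcomes:** keep the all-participant contrast as the main field result. Beside it, pre-specify the Condition 2 versus Condition 4 contrast among participants with e-liquid in the no-NNC basket of either condition. State that the indicator uses both baskets, not the one received. Report the share of participants who meet it.
- **In-Person Lab Visit 2:** refer to the same pair of contrasts for withdrawal, craving, satisfaction and carbon monoxide.
- **Virtual Visits 2-5:** stratify the random draw of the field condition on this indicator, and state that the draw is made after Virtual Visit 5, when the indicator is known.
- **While editing the model sentence:** flavor is constant across Conditions 2 and 4, so a flavor main effect and an interaction cannot be estimated from the field data. The allocation text and the model text need to be reconciled on this separate point.

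The cost is some added analysis wording, one extra exploratory contrast on fewer people, and one stratification variable at the draw. No new data are needed.
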